5.3. Method of Assignment to Treatment

Patients who meet all criteria for enrollment will be randomized at Visit 2. Assignment to treatment groups will be determined by a computer-generated random sequence using an interactive web-response system (IxRS). The IxRS will be used to assign the package containing double-blind investigational product to each patient. Site personnel will confirm that they have located the correct package by entering a confirmation number found on the packages into the IxRS.

To achieve between-group comparability for site, the randomization will be stratified by site.

This is a double-blind study, with a Placebo-Controlled period and a period without placebo (Delayed-Start period). Both patients and site personnel are to remain blinded to dose and prior allocation of placebo throughout the study.

To preserve the blinding of the study, a minimum number of Lilly personnel will see the randomization table and treatment assignments before the study is complete.

Controlled and Delayed-Start periods, placebo followed by LY3314814 20 mg, or placebo followed by LY3314814 50 mg in a ratio of 2:2:1:1. If a subject withdraws from the study, the subject's screening and randomization code will not be reused, and the subject will not be allowed to reenter the study. The IxRS will be used to assign a dosing regimen to each patient.

6. A Priori Statistical Methods

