6.2. Adjustments for Covariates

Repeated measures models will include the fixed, categorical effects of treatment, visit (treated as a categorical variable), treatment-by-visit interaction, pooled site, and concomitant AChEI and/or memantine use at baseline (yes/no), as well as the continuous, fixed covariate of baseline, baseline-by-visit interaction and age at baseline.

When an analysis of covariance (ANCOVA) model is used to analyze a continuous efficacy or safety variable, the model will contain the main effects of treatment, pooled site, concomitant AChEI and/or memantine use at baseline (yes/no), and the appropriate baseline value as a covariate.

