6.12. Efficacy Analyses

6.12.1. Placebo-Controlled Treatment Period

6.12.1.1. Primary Efficacy Analysis

The primary objective of this study and of the Placebo-Controlled period is to test the hypothesis that at least one dose of LY3314814 will slow the clinical decline of AD as compared to placebo in patients with mild AD dementia. This objective will be assessed on the Evaluable – PC population using an MMRM analysis of the ADAS-Cog13 in patients with mild AD at baseline, in which the specific hypothesis is that the decline from baseline at the end of the placebo-controlled treatment period (78 weeks) for at least one dose of LY3314814 will be significantly less than that for placebo.

The change from baseline score on the ADAS-Cog13 at each scheduled postbaseline visit (according to the Study Schedule) during the Placebo-Controlled period will be the dependent variable. The model for the fixed effects will include terms for: baseline score, pooled site, treatment, visit, treatment-by-visit interaction, baseline-by-visit interaction, concomitant AChEI and/or memantine use at baseline (yes/no), and age at baseline. Visit will be considered a categorical variable with values equal to the visit numbers at which the ADAS Cog13 was assessed.

The null hypothesis is that the contrast between both LY3314814 dose groups versus placebo at the last visit equals zero. An unstructured covariance matrix will be used to model the within-subject variance-covariance structure. If the unstructured covariance matrix results in a lack of convergence, the following tests will be used in sequence: heterogeneous Toeplitz covariance structure, heterogeneous autoregressive covariance structure, heterogeneous compound symmetry covariance structure.

The Kenward-Roger approximation will be used to estimate the denominator degrees of freedom.

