6.15. Subgroup Analyses

To assess the effects of various demographic and baseline characteristics, subgroup analyses will be performed for the primary endpoint for the Placebo-Controlled period based on the following variables:

- Age ≥ 55 and < 72 or ≥ 72 and < 85
- APOE4 carrier status (carrier $[\epsilon 2/\epsilon 4, \epsilon 3/\epsilon 4, \epsilon 4/\epsilon 4]/\text{non-carrier})$
- Region US or OUS

The primary outcome measure for the Placebo-Controlled period will be modeled using a mixed model repeated measures (MMRM) approach. This general model will include terms for baseline, treatment, visit, concomitant AChEI/memantine use at baseline (yes/no), age (except when age is the subgroup being assessed), treatment by visit, subgroup by treatment, subgroup by visit, and treatment by visit and subgroup. Redundant terms will be dropped from the model in cases where the subgroup of interest overlaps with this general model.

All subgroup analyses presented will be exploratory.

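### The subgroup MMRM in SAP 6.15 omits pooled site (the randomization stratum) and baseline-by-visit, so subgroup effects are not adjusted in the same way as the overall effect

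*SAP*

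**What the plan says.** SAP 6.2 sets the general rule: "Repeated measures models will include the fixed, categorical effects of treatment, visit (treated as a categorical variable), treatment-by-visit interaction, pooled site", with AChEI and/or memantine use at baseline. It then adds "the continuous, fixed covariate of baseline, baseline-by-visit interaction and age at baseline". It states no exception.

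SAP 6.12.1.1 follows that rule for the primary ADAS-Cog13 analysis. Its list opens with "baseline score, pooled site, treatment, visit, treatment-by-visit interaction, baseline-by-visit interaction" and adds AChEI/memantine use and age. SAP 6.12.1.2 takes over the same eight effects for the secondary clinical outcomes.

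SAP 6.15 covers the same primary endpoint, also by MMRM, for three two-level factors: age band, APOE4 carrier status, and US versus outside the US. Its main terms are given as "This general model will include terms for baseline, treatment, visit, concomitant AChEI/memantine use at baseline (yes/no), age", with age left out when age is the subgroup. The interactions are "treatment by visit, subgroup by treatment, subgroup by visit, and treatment by visit and subgroup". One sentence allows changes to the list: "Redundant terms will be dropped from the model in cases where the subgroup of interest overlaps with this general model".

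SAP 5.3 describes the design: "To achieve between-group comparability for site, the randomization will be stratified by site". Protocol 7.2 says the same. Protocol 10.3.6.2 names the subgroup factors but gives no subgroup model.

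**The concern.** A subgroup estimate is normally read against the overall estimate. If the two come from models with different covariates, part of any gap between them reflects the adjustment and not the patients.

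Pooled site also represents the only stratification factor the plan names, and a model for the primary endpoint would ordinarily carry it. Without baseline-by-visit, the baseline slope is forced to be the same at every visit, which is a stronger assumption than the primary model makes.

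There is also a plain drafting problem. A programmer who follows 6.2 and one who follows 6.15 will fit different models and report different numbers for the same table.

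**Working it through.** **1. Figures the plan states.** The documents give no figure for the subgroup model, so there is none to reproduce. The sample-size figures (Protocol 10.1, SAP 5.2) do reproduce:
- A two-sided t-test with effect size 0.212, alpha 0.025 and 90% power needs 554 completers per arm.
- 554 / (1 - 0.25 × 0.50) = 554 / 0.875 = 633.1, stated as 633; 3 × 633 = 1899.
- Power for ADAS-Cog13 (2.91, SD 10.84) at 633 per arm is 99.43%, stated as 99.4%.

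None of these depends on the subgroup model.

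**2. The three term lists side by side.**

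| Fixed effect | SAP 6.2 | SAP 6.12.1.1 | SAP 6.15 |
|---|---|---|---|
| Baseline | yes | yes | yes |
| Treatment | yes | yes | yes |
| Visit | yes | yes | yes |
| Treatment-by-visit | yes | yes | yes |
| AChEI/memantine at baseline | yes | yes | yes |
| Age at baseline | yes | yes | yes, unless age is the subgroup |
| Pooled site | yes | yes | **no** |
| Baseline-by-visit | yes | yes | **no** |

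Six of the eight effects carry over and two do not. The sentence on redundant terms can only remove terms, so it cannot restore these two.

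**3. Site alone, rough size.** If pooled site explains a share R² of the residual variance, leaving it out multiplies the standard error by about 1/√(1 - R²). R² is an assumption, since the documents give no site variance.
- R² = 0.02: 1/√0.98 = 1.010
- R² = 0.05: 1/√0.95 = 1.026
- R² = 0.10: 1/√0.90 = 1.054

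This ignores the degrees of freedom spent on site effects.

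**4. Both terms together, by simulation.** Taken from the plan: N = 1899, SD 10.84, effect -2.91. Assumed: 150 sites, site-stratified allocation, a balanced two-level subgroup, 74% of patients observed at the last visit, and the site shares and slopes below. There were 40 simulated trials per setting. The target is one active arm against placebo within one subgroup level at Week 78.

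| Site share, baseline-by-visit slope | Mean estimate with / without the two terms | Model SE with / without | Mean SE ratio, without/with | SD of within-trial difference | Correlation of estimates |
|---|---|---|---|---|---|
| 0, 0 | -2.99 / -3.01 | 0.975 / 0.970 | 0.995 | 0.08 | 0.995 |
| 5%, 0.2 | -3.09 / -3.12 | 0.955 / 0.973 | 1.019 | 0.17 | 0.98 |
| 10%, 0.4 | -2.90 / -2.95 | 0.925 / 0.981 | 1.061 | 0.31 | 0.97 |

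The SE ratio runs from about 1.00 to 1.06. The mean shift is at most 0.05 points, against an SE of about 0.95. In a single trial the two models typically differ by 0.08 to 0.31 points (one SD). With 40 trials per setting, this indicates the order of magnitude and no more.

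**5. Would the terms be estimable?** Age band and APOE4 status vary between patients within a site, so a site term does not alias them. For US/OUS, SAP 6.4 pools small sites only within country, so each pooled site lies in one region. The site term then absorbs the region main effect, while treatment-by-region and the terms involving visit remain estimable.

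**The case against.** The strongest reply is that 6.2 is only a default. The SAP also lists MMRMs without site or baseline-by-visit for laboratory values (6.13.4), ECG (6.13.6), plasma Aβ (6.14.1) and tau PET (6.14.5), so 6.15 may be one more section with its own list. That is a fair account of the drafting, but those outcomes are safety measures and biomarkers. The clinical efficacy MMRMs in 6.12 keep all eight effects. 6.15 is the one that drops two of them, on the primary endpoint, without giving a reason. Nor does 6.2 say that later sections may override it.

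A second reply is that site is awkward for US/OUS, because it is nested in region. That is true of the region main effect only, and it does not explain the omission for age or APOE4.

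A third is that nothing depends on these analyses. SAP 6.15 calls them exploratory. After the futility stop, SAP 6.1 says no test will be interpreted as statistically significant, and 6.1.1 treats all results as hypothesis-generating. This stands, and it sets the severity.

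Three stronger readings might be inferred, and the documents support none of them:
- *That subgroup and overall results cannot be compared, or that the subgroup effects are biased.* Both models are linear models of the same change score in a randomized trial and target the same Week 78 difference. The illustration shows no material shift.
- *That the absence of a subgroup main effect from the list is a further error.* With three arms, six visits and two subgroup levels, the listed terms already span all 3 × 6 × 2 = 36 cells. The design rank is 36 with or without the main effect, so the fit is the same.
- *That the subgroup intervals are certainly too wide.* That depends on a site variance the documents do not give. With no site effect and no baseline-by-visit slope, nothing is lost.

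**Conclusion.** The point holds as an internal inconsistency with a small practical cost. SAP 6.15 models the primary endpoint without two effects that 6.2 requires and 6.12.1.1 includes. One of them represents the randomization stratum, and no other section restores them. The term comparison is certain.

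The size is not certain. An SE about 0-6% larger rests on assumed site shares of 0-10%, assumed slopes of 0-0.4, an assumed 150 sites and the planned sample size. The number of patients with Week 78 data after the early stop is not in the documents. The consequence is unequal adjustment and perhaps a slight loss of precision, with no bias shown. Severity is low.

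**What to change.** Rewrite the model in SAP 6.15 as the 6.12.1.1 model, with pooled site and baseline-by-visit, plus the subgroup terms. Naming the subgroup main effect is optional tidying and does not change the fit. Add a line for US/OUS saying that pooled site absorbs the region main effect and that the contrast of interest is treatment-by-region at Week 78.

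If the shorter model was intended, state in 6.2 that 6.15 is an exception and give the reason. In either case, a sentence in 6.2 saying which analyses use reduced models would also settle the safety and biomarker lists.

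The cost is SAP wording and a small change to the subgroup program. Pooled site and the baseline score are already derived for the primary analysis, no further data are needed, and no sample size, power or alpha figure changes.

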6.16. Protocol Violations

Listings of subjects with significant protocol violations will be provided for the Randomized Population.

The following list of significant protocol violations will be programmed against the clinical database:

- Informed consent violation detected as a missing date of informed consent
- Did not have an assessment of the primary endpoint at any of the visits at which the scale was scheduled to be assessed
- Not compliant with study drug calculated as taking less than 80% or greater than 120% of study drug while the subject was expected to be on treatment

The following list of significant protocol violations will be determined by clinical/medical group:

Protocol violations of inclusion/exclusion criteria

- Study dosing algorithm violation (such as if subjects randomized to treatment A were given treatment B or subjects randomized to treatment A never received the assigned study drug.)
- Unqualified raters for the primary endpoint

Other protocol violations reported through the monitoring process will be reviewed by the study team and if judged to be significant, will be added to the final reported listing.

6.17. Interim Analyses and Data Monitoring

An independent data monitoring committee (IDMC) will have the responsibility to review accumulating unblinded study data on a periodic basis and make recommendations to protect the safety of study participants. Each member of the IDMC is a recognized expert in the fields of AD, neurology, cardiology, or biostatistics. All members will be external to the Sponsor. The approved IDMC charter enumerates the roles of the IDMC members, the frequency with which it meets, and the structure of their meetings. A statistical analysis plan (SAP) for analyses associated with the IDMC outlines the specific analyses that the IDMC will review.

An interim futility analysis may be conducted by the IDMC, for example, if study I8D-MC-AZES (AZES) is stopped for futility at an interim analysis. The purpose of this potential interim analysis for AZET is to potentially stop the study for futility.

Only the IDMC is authorized to evaluate unblinded interim efficacy and safety analyses. Study sites will receive information about interim results only if they need to know for the safety of their patients.

Study AZET will not be stopped early for efficacy.

6.17.1. Potential Futility Interim Analysis if Study AZES Proves Futile

A futility interim analysis may be performed if study I8D-MC-AZES fails its futility interim analysis.

6.17.1.1. Data Included in Futility Analysis

The Bayesian predictive probability of statistical significance for the 50 mg dose vs. placebo and the 20 mg dose vs. placebo at Week 78 will be calculated for the ADAS-Cog13 and iADL endpoints. The Bayesian predictive probability will be calculated from a Bayesian joint model of ADAS-Cog₁₃ and ADCS-iADL scores using diffuse priors.

For the patients included in the interim analysis data set, all available scores from ADAS-Cog13 and ADCS-iADL will be utilized. This will potentially include data from an individual patient at weeks 0, 13, 26, 39, 52, 65, and 78 for ADAS-Cog13, and weeks 0, 26, 52, and 78 for ADCS-iADL. A response vector is formulated for the observed scores from all patients in the interim analysis set, including the week 0 baseline assessment, for both the ADAS-Cog13 and the ADCS-iADL. If a patient has a missing value at a visit, or has not progressed in the trial to a visit, a missing value indicator (an NA) is included in the response vector for all missing visits.

The purpose of including the 'NA' values at missing visits is that it enables the prediction of the missing values which are provided in a very convenient fashion in the Bayesian framework.

6.17.1.2. Joint Model

The primary purpose of the joint model is to obtain a distribution of predicted values of ADAS-Cog13 and iADL at week 78 for patients that do not have observed values at week 78. The key features of the model are that it assumes linearity for both ADAS-Cog13 and ADCS-iADL, and that it includes subject specific intercepts and slopes for both ADAS-Cog13 and ADCS-iADL. The linearity assumption is reasonable based on current understanding of the progression of Alzheimer's Disease and is necessary due to the fact that fewer patients will have data available at week 78 at the timing of this futility analysis. The predicted values at week 78 are obtained assuming the same trend observed at this futility analysis will continue for all data collected through the end of the trial. The model is a 'joint' model since the overall error terms for ADAS-Cog13 and ADCS-iADL are allowed to be correlated in a 2 by 2 variance-covariance matrix, and the subject-specific random slopes and intercepts for ADAS-Cog13 and ADCS-iADL are allowed to be correlated in a 4 by 4 variance-covariance matrix. No structure is imposed on either of the variance-covariance matrices. The OpenBugs code that will be used to fit the joint model is provided below.

```
## OpenBugs code for the Bayesian joint model
    for (i in 1:Ntotal) {
        Y[i, 1:2] ~ dmnorm(mu[i, 1:2], omega[, ])
        mu[i, 1] <- b[subject[i], 1] + (b[subject[i], 2] + Beta5 *</pre>
             LY1[i] + Beta6 * LY2[i]) * time[i]
        mu[i, 2] <- b[subject[i], 3] + (b[subject[i], 4] + Beta7 *</pre>
            LY1[i] + Beta8 * LY2[i]) * time[i]
    }
    for (j in 1:Nsubj) {
        b[j, 1:4] ~ dmnorm(Beta.re[j, ], omega.re[, ])
        Beta.re[j, 1] <- Beta1</pre>
        Beta.re[j, 2] <- Beta2</pre>
        Beta.re[j, 3] <- Beta3</pre>
        Beta.re[j, 4] <- Beta4</pre>
    }
    Beta1 ~ dnorm(30, 0.005)
    Beta2 \sim dnorm(6.9, 0.005)
    Beta3 ~ dnorm(44, 0.005)
    Beta4 \sim dnorm(-6.9, 0.005)
    Beta5 \sim dnorm(0, 0.005)
    Beta6 \sim dnorm(0, 0.005)
    Beta7 \sim dnorm(0, 0.005)
    Beta8 \sim dnorm(0, 0.005)
    omega[1:2, 1:2] \sim dwish(R[, ], 2)
    sig[1:2, 1:2] <- inverse(omega[, ])</pre>
    R[1, 1] < -1
    R[1, 2] < -0
    R[2, 1] < -0
    R[2, 2] < -1
```

```
omega.re[1:4, 1:4] \sim dwish(R.re[, ], 4)
sig.re[1:4, 1:4] <- inverse(omega.re[, ])</pre>
R.re[1, 1] < -10
R.re[1, 2] <- 0
R.re[1, 3] <- 0
R.re[1, 4] <- 0
R.re[2, 1] <- 0
R.re[2, 2] <- 10
R.re[2, 3] <- 0
R.re[2, 4] <- 0
R.re[3, 1] < -0
R.re[3, 2] <- 0
R.re[3, 3] < -10
R.re[3, 4] <- 0
R.re[4, 1] <- 0
R.re[4, 2] <- 0
R.re[4, 3] <- 0
R.re[4, 4] < -10
```

The model includes generally diffuse priors on all parameters. For the parameters that estimate the mean baseline value for ADAS-Cog13 and ADCS-iADL (Beta1 and Beta3, respectively), the location parameter is defined to what is anticipated as the average baseline value for each scale. For the parameters that estimate the rate of decline for placebo at the end of the trial for ADAS-Cog13 and ADCS-iADL (Beta2 and Beta4, respectively), the location parameter is defined to what is anticipated as the overall rate of decline of placebo at week 78. The precision value for the prior distribution of all parameters is set to a small value; therefore, the prior distributions on all parameters have very little impact on the calculated predicted probability. The variable Ntotal has a value of 1 to 13,293 (1899 potential total patients x 7 visits). The variable Nsubj has a value of 1 to 1899. The variables LY1 and LY2 represent indicator variables for patients on the 20 mg and 50 mg doses, respectively. The variable time includes values of 0, 0.167, 0.33, 0.5, 0.667, 0.833, and 1, corresponding to the data collected at weeks 0, 13, 26, 39, 52, 65, and 78, respectively.

6.17.1.3. Calculating the Predicted Probability of ADAS-Cog13 and iADL

The joint model will be fit and a distribution of predicted values at week 78 for ADAS-Cog13 and iADL will be obtained. The single fitting of the joint model provides the predicted values at week 78 needed to create the predicted probability metric. The process used to generate the predicted probability is outlined in the following steps:

- 1. After a sufficient burn-in period, keep the collection of samples from the first iteration of the MCMC chain and obtain the week 78 predicted scores for patients that don't have an observed value for ADAS-Cog13 or iADL.
- 2. Merge the week 78 predicted scores with the values from patients that have observed data at week 78 to create a complete dataset of 1899 patients.
- 3. Calculate the change from baseline score as: week 78 score Week 0 baseline score.
- 4. Fit the following ANCOVA model: Change from baseline = baseline + 20 mg Treatment Indicator + 50 mg Treatment Indicator.

- 5. Store the test statistics corresponding to the contrast of the 50 mg dose vs. placebo and the 20 mg dose vs. placebo.
- 6. Repeat steps 1-5 50,000 times to generate 50,000 test statistics for the 50 mg vs. placebo contrast and the 20 mg vs. placebo (note that updated predicted values—where baseline or week 78 values were not observed—will be utilized for each iteration of the MCMC chain).
- 7. There are 4 predicted probabilities calculated, one for each scale at each doses. The predicted probability is calculated as the proportion of the 50,000 times that the change score on treatment is statistically significantly less than the change score of the placebo dose (at a 1-sided 0.0125 alpha level).

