# 9.1.2. Secondary Efficacy Assessments

Alzheimer's Disease Cooperative Study—Activities of Daily Living Inventory (ADCS-ADL; Galasko et al. 1997, 2004). The ADCS-ADL measures 6 basic and 17 instrumental activities of daily living and was specifically developed as a sensitive tool to track changes in functional performance in AD over time. The basic activities include self-care tasks such as eating, walking, toileting, bathing, and grooming. The instrumental activities are more complex skills that are required to successfully live independently and include shopping, keeping appointments, traveling outside of home, making a meal or snack, reading, and writing. These instrumental skills are often compromised in early AD.

For each activity on the ADCS-ADL, the score ranges from 0 to 78, with lower scores indicating greater impairment. The maximum basic items score (sum of individual basic item scores) is 22, and the maximum instrumental items score (sum of individual instrumental item scores) is 56 (Galasko et al. 2004).

Administration of the ADCS-ADL will be audio-recorded for quality-control and training purposes. Audio recordings will be centrally reviewed and monitored where permitted by local law.

Functional Assessment Questionnaire (FAQ; Pfeffer et al. 1982). The FAQ measures complex functional activities that may be impaired in AD (such as, ability to shop, cook, and pay bills). The FAQ is a study partner/informant rating of the performance changes in 10 complex activities of daily living and has an overall score range of 0 to 30, with the higher score indicating greater impairment.

The 10 complex activities include: 1) manage finances, 2) complete forms, 3) shop, 4) perform games of skill or hobbies, 5) prepare hot beverages, 6) prepare a balanced meal, 7) follow current events, 8) attend to television programs, books or magazines, 9) remember appointments, and 10) travel out of the neighborhood.

Administration of the FAQ will be audio-recorded for quality-control and training purposes. Audio recordings will be centrally reviewed and monitored where permitted by local law.

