### 10.3.3.3.2. Secondary MMRM Efficacy Analyses – Placebo-Controlled period

A secondary objective of the Placebo-Controlled period is to test the hypothesis that at least one dose of LY3314814 will slow the functional decline (ADCS-iADL and/or FAQ) and/or cognitive/functional outcomes (CDR-SB and/or iADRS) of AD compared with placebo in patients with mild AD. This will be assessed using MMRM analyses, in which the specific hypothesis is that the functional decline from baseline at the end of the treatment period (78 weeks) for at least one dose of LY3314814 will be significantly less than that for placebo. The MMRM model used in the primary analysis will also be employed for these key secondary analyses.

Similar to the primary analysis, each of the additional secondary efficacy outcomes will be assessed using an MMRM analysis. These secondary efficacy outcomes include MMSE and NPI. For each secondary efficacy measure, the change from baseline score at each scheduled postbaseline visit (according to the Study Schedule) during the Placebo-Controlled period will be analyzed using the same MMRM model described for the primary analysis.

An additional MMRM analysis, termed a slopes analysis, will be conducted examining the change from baseline score on the ADAS-Cog13, ADCS-iADL, and FAQ at each scheduled postbaseline visit. In contrast to the primary analyses which considered visit (time) as a categorical variable, time from randomization in this analysis will be treated as a continuous variable. The model for the fixed effects will include baseline score, pooled investigator, treatment, time, treatment-by-time interaction, concomitant AChEI and/or memantine use at baseline (yes/no), and age at baseline. The treatment-by-time interaction term will be examined to assess whether each LY3314814 treatment group and placebo have differing slopes in terms of ADAS-Cog13, ADCS-iADL, or FAQ progression. The effect of a quadratic term for time (and its associated interaction with treatment) on the model will also be examined.

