AZET (The DAYBREAK Study) is a randomized, double-blind, placebo-controlled study of LY3314814 in patients with mild Alzheimer's Disease (AD) dementia and abnormal levels of amyloid, consisting of a 78 week Placebo-Controlled period followed by a 78 week Delayed-Start period. Study AZET was deemed to be futile and stopped on June 12, 2018. Because of this futility, the original planned delayed-start analysis of evaluating disease modification of LY3314814 by summarizing both efficacy and safety across both study periods became moot. Analyses of study AZET will be separated by study period: placebo-controlled study period and the delayed start study period.

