6.17.1.4. Futility Threshold

Each of the four predictive probabilities will be compared to 0.465. In order to pass the futility threshold, the predictive probabilities for ADAS-Cog13 and iADL must be greater than 0.465 for at least one dose. A futility threshold of 0.465 has the following operating characteristics:

- If the assumed effect size is 0, 90.1% of the trials that would fail if the study were run to completion would be stopped by this futility threshold;
- If the assumed effect size is 0.11, 21.4% of trials that would succeed if the trial were run to completion would be stopped by this futility threshold.

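### SAP 6.17.1.3 step 7 counts a significantly lower change score as success on both scales; on ADCS-iADL that is harm, so the futility rule is wrong as written

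*SAP*

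**What the plan says.** SAP 6.17.1.3 builds the predictive probabilities in seven steps. Step 3 forms the change from baseline to Week 78, step 4 fits an ANCOVA with two dose indicators, and step 5 keeps the test statistics for each dose against placebo. Step 7 defines four probabilities (two scales, two doses), each being the proportion of 50,000 draws in which the "change score on treatment is statistically significantly less than the change score of the placebo dose (at a 1-sided 0.0125 alpha level"). No separate direction is given for either scale.

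SAP 6.17.1.4 sets the pass rule: "In order to pass the futility threshold, the predictive probabilities for ADAS-Cog13 and iADL must be greater than 0.465 for at least one dose". It gives two operating characteristics. At effect size 0, the threshold stops 90.1% of trials that would fail. At effect size 0.11, "21.4% of trials that would succeed if the trial were run to completion would be stopped by this futility threshold".

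The scales run in opposite directions. Protocol 9.1.1 scores ADAS-Cog13 so that lower is better. Protocol 9.1.2 scores ADCS-ADL "with lower scores indicating greater impairment". The joint model in SAP 6.17.1.2 keeps both in raw direction: the placebo slope prior is "dnorm(6.9, 0.005") for ADAS-Cog13 and has mean −6.9 for ADCS-iADL. The text after the code describes these two parameters as "the rate of decline for placebo at the end of the trial for ADAS-Cog13 and ADCS-iADL (Beta2 and Beta4, respectively").

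**The concern.** A single signed criterion cannot mean benefit on two oppositely scored scales. With change taken as Week 78 minus baseline, a treatment change below placebo is slower decline on ADAS-Cog13 and faster decline on ADCS-iADL. Nothing in SAP 6.17 reverses iADL. Because the pass rule needs both scales, one wrong sign disables the whole rule: the better the drug works on function, the less likely it is to pass.

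SAP Section 4 reports that "Study AZET was deemed to be futile and stopped on June 12, 2018". If step 7 was programmed as written, the iADL probability was the chance of a significantly worse functional result. If it was programmed for benefit, the SAP misdescribes its own stopping rule. The documents give code for the joint model only, so a reader cannot tell which applies.

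**Working it through.** **Inputs.** From SAP 5.2: 633 per group with placebo pooled; effect sizes 2.91/10.84 (stated as 0.269) for ADAS-Cog13 and 2.07/9.78 = 0.212 for ADCS-iADL. From SAP 6.17.1.3: one-sided alpha 0.0125, so z = 2.241. From SAP 6.17.1.4: threshold 0.465, both scales, at least one dose. The documents do not give the interim information fraction t, the correlation ρ between scales, or the definition of a trial that would succeed. I varied all three.

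**The plan's own figures.** The sample size reproduces: Φ(0.2117 × √(554/2) − 2.241) = 90.0% for iADL with 554 per arm, and 554/(1 − 0.25 × 0.50) = 633. ADAS-Cog13 power at 633 is 99.4%, as stated. The 21.4% cannot be recomputed exactly, because the three unstated quantities enter it.

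**Direction by scale.**

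| Scale | Worsening | Placebo slope prior | Treatment change below placebo means |
|---|---|---|---|
| ADAS-Cog13 | score rises | +6.9 | benefit |
| ADCS-iADL | score falls | −6.9 | harm |

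I read step 3 as Week 78 minus baseline; the operator is not visible in the text available to me. The conclusion does not depend on it: the opposite subtraction would make a lower change mean harm on ADAS-Cog13 instead.

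**Final analysis, iADL, one dose.** The expected Z is d × √(633/2) = 17.79d.

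- d = 0.212: expected Z = 3.772. Benefit direction: Φ(3.772 − 2.241) = 93.7%. As written: Φ(−3.772 − 2.241) = 9 × 10⁻¹⁰.
- d = 0.11: expected Z = 1.957. As written: Φ(−1.957 − 2.241) = 1.3 × 10⁻⁵.

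**Interim rule.** I simulated 400,000 trials per cell: four correlated Brownian-motion Z statistics (two doses, two scales), with correlation 0.5 between doses from the shared placebo group. With a flat prior, PP = Φ((B/t − 2.241)/√((1 − t)/t)), where B is the Brownian value at t. A trial passes if PP > 0.465 on both scales for the same dose. The drug effect is beneficial on both scales throughout; only the iADL test direction changes. The table covers t = 0.1–0.5 and ρ = 0–0.6.

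| Quantity | As written | Benefit direction | SAP |
|---|---|---|---|
| Design effects: all trials stopped | 94.9–100% | 5–24% | – |
| Effect 0.11: stopped among would-succeed, both scales at one dose | 93–100% | 27–49% | 21.4% |
| Effect 0.11: stopped among would-succeed, ADAS-Cog13 alone | 89–100% | 38–57% | 21.4% |
| Effect 0: stopped among would-fail | 88–100% | 76–99% | 90.1% |

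With t extended to 0.8 and success defined on both scales, the benefit direction reaches about 21% (t = 0.7, ρ = 0.6; also t = 0.8, ρ = 0.2). The literal rule never falls below 89%. The 90.1% is compatible with either direction.

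**Limits.** No single cell returned 90.1% and 21.4% together. Where the effect-0.11 figure is near 21%, the effect-0 figure is about 99% or more; where the effect-0 figure is near 90% (t = 0.3, ρ = 0.6: 91%), the effect-0.11 figure is 32%. This is no evidence against the SAP's figures, because the approximation is not their joint model. The result does depend on the two-scale requirement: if any one of the four probabilities were enough, which is not what 6.17.1.4 says, the literal wording would stop roughly 24–30% of would-succeed trials.

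**The case against.** The strongest reply is that this is loose wording with an obvious meaning. The plan's hypotheses are about decline: Protocol 10.3.3.3.2 words its comparison with placebo as "functional decline from baseline at the end of the treatment period (78 weeks) for at least one dose of LY3314814 will be significantly less", and SAP 6.17.1.2 calls both the +6.9 and the −6.9 slope a decline. On that view, step 7 means less decline and was programmed so. As a statement of intent this is probably right. It does not repair the text: step 7 is a numbered computing instruction about a signed change score, not about decline.

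Three further objections deserve an answer.

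- The documents say only that an AZET futility analysis may be run, and SAP 6.17 refers to a separate analysis plan for the data monitoring committee, which may state the contrasts. This stands as a caution: the documents do not prove that step 7 was executed or drove the stop. But SAP Version 2 was approved for that potential interim, and SAP 6.7 attributes discontinuations to a sponsor decision after the futility analysis, so asking which sign was used is reasonable.
- SAP 6.17.1.4 does not give the sign of the simulated 0.11 effect. If the sponsor simulated an iADL effect in the same direction as the rule, 21.4% would look the same either way. This is true, and it is why the simulation sign also needs documenting.
- Version 3 of the SAP was written after the stop and treats all results as non-confirmatory, so a correction changes no reported analysis. That limits the urgency, not the need for a reproducible stopping rule.

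**Conclusion.** The concern holds. Step 7 gives the wrong criterion for ADCS-iADL, and this follows from the text alone, without simulation. Followed literally, the two-scale rule would stop 94.9–100% of trials at the design effects. At effect 0.11 it would stop 89–100% of trials that would succeed, against the SAP's 21.4%. Those interim ranges rest on assumed information fractions and correlations, a flat-prior Brownian approximation, and a drug that benefits both scales.

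The balance of evidence points to a wording error with the threshold calibrated for benefit. The documents do not show that the wrong sign was run, and I do not claim that it was. This should be fixed because it concerns the futility stopping rule of a study that was stopped for futility.

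**What to change.** Reword step 7 by scale: for ADAS-Cog13, count draws where the treatment change is significantly less than placebo; for ADCS-iADL, count draws where it is significantly greater (less decline). Record in the SAP or the clinical study report the contrast sign used for iADL in the 2018 interim, if it was run, and the effect and contrast signs used in the simulations behind 90.1% and 21.4%. Recompute the four probabilities only if the executed iADL sign proves to have been reversed.

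The cost is one sentence in the SAP and a check of existing code. No new data are needed.
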